**SUMMARY SCHEDULE OF EVENTS**

Date Due at OCTO (time after randomisation)	CRFs Due	Samples Due
5 years	5 year Follow-up	
Between 4 and 6 years		Blood sample
6 years (+/- 3 months)	6 year Follow-up Endoscopy and Pathology Biopsy Sampling	Endoscopy Biopsy samples
7 years	7 year Follow-up	
8 years (+/- 3 months)	8 year Follow-up Endoscopy and Pathology Biopsy Sampling End of Treatment (if not re-consented to 10 years follow up)	Endoscopy Biopsy samples Blood sample
9 years (only if patient consented for 10 years follow up)	9 year Follow-up	
10 years (+/- 3 months) (only if patient consented for 10 years follow up)	10 year Follow-up Endoscopy and Pathology Biopsy Sampling End of Treatment	Endoscopy Biopsy samples Blood sample
Unscheduled	Serious Adverse Event Death (when no causal relationship with trial medication is suspected) End of Treatment (for patients who withdraw from treatment early) Consent Withdrawal Notification (for patients who withdraw from all parts of the study) Change of Treatment Additional Data (for any other information you feel necessary to report or if you need more space to continue on from another CRF) Endpoint Sampling (for patients with low or high grade dysplasia or oesophageal adenocarcinoma) Pregnancy Notification Bowel Screening Clopidogrel	

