## 6.5 Death

If a patient dies, an End of Treatment Form and a Death Form should be completed and sent to the Trial Office immediately. Deaths resulting from SAEs must be reported on the trial SAE report form instead of the Death Form.

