### **10 ASSESSMENT OF SAFETY**

The Investigator must monitor each patient for clinical and laboratory evidence of adverse events at each contact with the participant throughout the study. During the course of the annual Follow Up, all patients should be asked directly if they have had any hospital admissions or events which should be reported as a SAE (see definition in Section 10.1). Their patient notes should also be checked for such occurrences. All SAEs should be reported to the Trial Office as described in Section 10.4.

Adverse event monitoring starts from the time the patient commences study medication until they complete the trial. An SAE which occurs more than 30 days after a patient has stopped taking trial medication is not required to be reported, unless the event is related to a trial procedure (e.g. biopsy or blood collection). All SAEs will be followed to a satisfactory conclusion. Any SAEs that are unresolved at the patient's last visit in the study are followed up by the Investigator for as long as medically indicated.

All SAEs reported to the Trial Office will be processed according to internal SOPs. The Trial Office may request additional information for any SAE as judged necessary.

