### **Death on study**

Provided it is not as a result of an SAE, then a death during the course of the study should be recorded on the Death CRF. Deaths arising from SAEs should be reported using the SAE Form.

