2.7 Definition of Primary and Secondary Outcomes

Primary outcome is

- Time from randomisation date to conversion from Barrett's metaplasia to high grade dysplasia (event), or to adenocarcinoma of the oesophagus (event) or time to death from all causes (event) or time to last follow-up (no event)

I.e. the time is noted as the time from date of randomisation to high grade dysplasia, adenocarcinoma of the oesophagus or death, whichever is the earlier, with the survival time coded as an event. For patients who do not have one of these events of interest, the time from randomisation to date of last follow-up is calculated and the survival time coded as a censored event.

Secondary outcomes are

- Time from randomisation date to conversion from Barrett's metaplasia to high grade dysplasia (event) or time to last follow-up (no event) or event that precludes getting high grade dysplasia (for example death) (no event)
- Time from randomisation date to progression from Barrett's metaplasia to adenocarcinoma of the oesophagus (event) or time to last follow-up (no event) or event that precludes getting adenocarcinoma of the oesophagus (for example death) (no event)
- Time from randomisation date to death from all causes (event) or time to last follow-up (no event)
- Time from randomisation date to death from oesophageal cancer (event) or time to last follow-up (no event) or death from a cause other than oesophageal cancer (no event)
- Molecular markers to be identified at the end of the trial and used during analyses of collected blood and/or tissue samples
- Cost per oesophageal adenocarcinoma prevented

AspECT

A phase III randomised study of Aspirin and Esomeprazole chemoprevention in Barrett's metaplasia

Funded by CR-UK, MRC, UHL and NCI

ISRCTN No.85156844

- Cost per life year saved
- Molecular markers to be identified at the end of the trial and used with samples collected across time along with treatment information
- Cost per quality adjusted life saved
- Cardiac event from SAE (our best data on cardiac disease) and new tumours (a marker of aspirin resistance)
- For gender secondary, same outcome as for primary

AspECT

A phase III randomised study of Aspirin and Esomeprazole chemoprevention in Barrett's metaplasia

Funded by CR-UK, MRC, UHL and NCI

ISRCTN No.85156844

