6.6 Description of Available Data

Primary endpoint – survival until adenocarcinoma, high grade dysplasia or death from any cause

There will be a time for every patient. For some of the patients who do not reach an endpoint, the survival time will be less than the trial duration due to loss to follow-up. The endpoint of death and diagnosis of Barrett's adenocarcinoma can be picked up in many cases from NHS digital but the endpoint of high grade dysplasia will be under represented due to those lost to follow-up.

The median follow-up will be described using the median of those without an event and the median using the reverse Kaplan-Meier method.

Kaplan-Meier curves will be drawn for all patients, then split by aspirin intervention and split by PPI dose (low or high).

The analysis of the primary objective involves knowledge of the treatment and then knowledge of the factors used in the minimisation which will be available for everyone from the randomisation.

AspECT

A phase III randomised study of Aspirin and Esomeprazole chemoprevention in Barrett's metaplasia

Funded by CR-UK, MRC, UHL and NCI

ISRCTN No.85156844

Secondary endpoints –adenocarcinoma, high grade dysplasia, death
As described for primary but for each event separately.

Secondary endpoints – clinical and molecular risk factors

Available for a varying number of patients

Secondary endpoint - cost effectiveness

This endpoint is not being analysed by CSM

Secondary endpoints - changes in molecular markers and genomics

This endpoint is not being analysed by CSM

Secondary endpoints – quality of life

It was not possible to collect this data across time so this analysis cannot be done

Secondary endpoints – biological risk factors for cardiac disease and aspirin resistance

Cardiac events fulfilling a seriousness criterion will be noted as SAE and this will be used as indicative of cardiac disease. Biological risk factors of hypercholesterol, family history, patient's history, hypertension, diabetes and smoking will be tabled to show availability of this data.

Secondary endpoints – gender effect

Gender data should be available on all from randomisation

Sensitivity analysis – presence of helicobacter will be defined as helicobacter seropositivity at any point in the trial.

Pathology – local pathology results will be used

7. Patient Groups for Analysis

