An economic analysis will be undertaken which compares the mean per patient cost of the alternative trial arms using resource use data collected in the trial and appropriate UK unit costs. Differential costs could then be related to conversion to BA. To increase the value to decision makers, the economic data collected in the trial could be synthesised with other evidence by relating long-term (lifetime) health service costs to long-term quality-adjusted life expectancy. The analysis would be based on a state transition model, which would characterise how patients progress from BM to dysplasia and to BA competing risk of death. The annual cost and health-related quality of life associated with each stage of the disease will be estimated using trial data collected and literature. In addition, some limited data collection in appropriate non-trial patients would be undertaken. Assessments will be completed at baseline and every two years at the time of endoscopy.

- To assess whether intervention with PPI and/or aspirin induces changes in the expression of molecular markers for BA. To assess the genomics of aspirin sensitivity (efficacy and side effects)

ANALYSIS: Based on analysis of the samples, this aim will be carried out after the end of the trial under a separate analysis plan.

- To assess how quality of life is affected by the different treatments.

It was not possible to collect quality of life across time and so this secondary cannot be completed.

AspECT

A phase III randomised study of Aspirin and Esomeprazole chemoprevention in Barrett's metaplasia

Funded by CR-UK, MRC, UHL and NCI

ISRCTN No.85156844

- We will also assess what the biological risk factors are for cardiac disease and aspirin resistance.

Cardiac disease will be ascertained from SAE. The risk factors to be tested are hypercholesterol, family history of cardiac disease, patient history of cardiac disease, hypertension, diabetes or smoking. A logistic model predicting cardiac disease using these factors will be built. To consider aspirin resistance, a logistic model predicting cardiac disease in those taking aspirin will be built and described.

These 2 models will be repeated for the data from the time of the new tumour questions using cancer instead of cardiac disease.

- To assess if gender is prognostic for conversion or survival

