9.1 Resource Use and Cost Data

The health economics data for this trial will not be analysed by CSM; the analysis will be undertaken by [name].

10. Exploratory analyses not specified prior to receiving data

Any analyses not specified in this document will be exploratory in nature.

11. Serious adverse events

Serious adverse events are defined as those that are fatal, life threatening, disabling, a congenital birth defect, another important medical event which require hospitalisation or prolongation of hospitalisation. Any serious adverse event occurring whilst a participant is continuing in the study, until trial medication is stopped will be recorded. All serious adverse events will be described in tables including causality, CTCAEgrade, outcome and seriousness. A comparison of specific serious adverse events between the treatment groups (aspirin vs no aspirin and low PPI vs high PPI) will be assessed by examination of 95% confidence intervals for the difference in incidence. An overall category for any serious adverse event will also be compared using the chi square test. The analysis will be conducted by intention to treat. An overall category for renal impairment (dehydration, renal, obstruction) will be compared using the chi square test.

SAE and death major bleeds will be summed and expressed as number of major bleeds per 1000 person years. 2 major bleeds per 10000 person years is expected.

12. Data from Canada

One site in Canada ran a trial of 50 patients using the same protocol. The entire analysis plan will be re-run including this data when it is available.

AspECT

A phase III randomised study of Aspirin and Esomeprazole chemoprevention in Barrett's metaplasia

Funded by CR-UK, MRC, UHL and NCI

ISRCTN No.85156844

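### The cardiac outcome is taken from SAE reports alone, so an unknown number of cardiac deaths can be coded as no cardiac disease

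*SAP*

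**What the plan says.** **Source of the cardiac outcome.** Three places in the SAP name SAEs and nothing else. Section 2.7 lists the outcome as "Cardiac event from SAE (our best data on cardiac disease". Section 6.6 states: "Cardiac events fulfilling a seriousness criterion will be noted as SAE and this will be used as indicative of cardiac disease". Section 9 repeats: "Cardiac disease will be ascertained from SAE". Section 9 then builds one logistic model for cardiac disease from clinical risk factors and a second, for aspirin resistance, among those taking aspirin.

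**Which form a death goes on.** The protocol's Summary Schedule of Events lists the Death form as "Death (when no causal relationship with trial medication is suspected". Section 6.5 uses a different test: "Deaths resulting from SAEs must be reported on the trial SAE report form instead of the Death Form". Section 10.8 agrees with 6.5: "Deaths arising from SAEs should be reported using the SAE Form".

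**Reporting window.** Protocol section 10 says: "An SAE which occurs more than 30 days after a patient has stopped taking trial medication is not required to be reported", with an exception for events related to a trial procedure. SAP section 11 describes a shorter period that ends when trial medication stops.

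**Contrast.** For major bleeds, SAP section 11 draws on both sources: "SAE and death major bleeds will be summed".

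**The concern.** If a cardiac death is not on an SAE form, the cardiac outcome does not see it. Because the models are logistic, with a yes/no outcome, that patient is then coded as free of cardiac disease and counted among the non-cases.

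Three things are at stake:

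- The risk-factor and aspirin-resistance models in SAP section 9 may misclassify some patients who had the most serious form of the outcome.
- The tables of fatal SAEs in SAP section 11 may be incomplete. Treatment is open (SAP 2.6.2), so under the schedule's rule a death's place in those tables depends on an unblinded causality judgement.
- The SAP adds death records for bleeds but gives no reason for not doing so for cardiac events.

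**Working it through.** The plan states no figure on this point, so there is none to reproduce. The check is a side-by-side reading, followed by an illustration of scale.

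**Route 1: the form. Take a fatal infarction on treatment, judged unrelated to the drugs.**

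| Rule followed | Reasoning | In the cardiac outcome? |
|---|---|---|
| Protocol Summary Schedule of Events | No causal link suspected, so Death form | Not if the Death form is the only record |
| Protocol 6.5 and 10.8, read with 10.1 and 10.4 | 10.1 defines an SAE whatever its causality and lists death as a criterion; 10.4 has unrelated SAEs reported on a shortened SAE form; 6.5 and 10.8 send the death to the SAE form | Yes |

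The same death can be counted or missed, depending on which part of the protocol the site followed.

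**Route 2: the window. Take a cardiac death more than 30 days after stopping medication.** No SAE report is required, whichever form rule applies. The patient can still be in the analysis. Protocol 6.1 keeps patients who stop early in follow-up, and 6.4 does the same for those taken off drug for high grade dysplasia or adenocarcinoma. (Protocol 5.2 lists ending treatment among the events that end follow-up, which sits badly with 6.1 and 6.4.) SAP section 9 uses the ITT sample where possible, so in the risk-factor model this patient is a non-case.

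**Scale of route 1, as an illustration.** Inputs from the documents:

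- 2513 patients randomised (SAP 2.3; Protocol section 2 gives 2012 men and 501 women)
- 1.16% annual mortality (Protocol 13.2; SAP 2.5.3)

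Expected deaths = 2513 × (1 − exp(−0.0116 × years)), ignoring loss to follow-up and ageing:

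- 8 years: 2513 × (1 − exp(−0.0928)) = 222.7, about 223
- 10 years: 2513 × (1 − exp(−0.116)) = 275.2, about 275

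The documents give neither the cardiac share of deaths nor the share recorded on the Death form only. Both are assumptions. Cardiac deaths missed over 8 years = 222.7 × cardiac share × Death-form-only share:

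| Assumed cardiac share | None on Death form only | Half | All |
|---|---|---|---|
| 10% | 0 | 11.1 | 22.3 |
| 20% | 0 | 22.3 | 44.5 |
| 30% | 0 | 33.4 | 66.8 |
| 40% | 0 | 44.5 | 89.1 |

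Over 10 years, the cardiac deaths at 10-40% number about 28-110. These are deaths, not misclassified patients: someone with an earlier cardiac SAE is already a case, so the last column is an upper limit for each share.

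**Scale of route 2.** The documents do not say how many patients stopped early or how long they were then followed, so no figure can be given.

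**The case against.** The strongest reply is that the protocol's reporting sections already capture these deaths. An SAE is defined regardless of causality, unrelated SAEs still go on the SAE form, and SAP section 11 names fatal events in its own SAE definition. Only a parenthesis in a summary list of forms points elsewhere. **This stands against a stronger reading.** A reader might infer that fatal cardiac events drop out altogether, or that the models rest on non-fatal events only. The documents do not support either: fatal cardiac events reported as SAEs are in the outcome, and the loss through form routing can be zero. The reply does not remove the conflict with the schedule, and it does not touch the reporting window.

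Other replies, and what stands of each:

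- **The limitation is disclosed**, since SAP 2.7 calls SAEs the best data available. True, but section 11 shows that death records can be added.
- **No arm comparison is at risk in the models.** Section 9 lists no treatment term, and the resistance model covers only those taking aspirin. This stands: differential causality judgement by arm bears on the SAE tables, not on these models, and no direction of bias for any risk factor can be shown.
- **Deaths are counted elsewhere.** This also stands. All deaths count in the primary endpoint and in all-cause mortality, both compared by arm.
- **Adding deaths is not automatic.** Appendix 2 lists cause of death without a source form. Flagging depends on patient agreement, and the documents describe it as supplying death and adenocarcinoma, not cardiac cause. Adding all late deaths while late non-fatal events go uncollected would create a new imbalance. These are fair limits, and the fix has to respect them.

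**Conclusion.** The concern holds in a limited form. The cardiac outcome rests on SAEs alone, and cardiac deaths can be missed because the death-form rules conflict and because required SAE reporting stops while follow-up continues. The second route is the firmer one, since it does not depend on which form rule a site followed.

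The number missed is unknown. Form routing could miss none, or up to about 22-89 deaths over 8 years if every cardiac death sat on a Death form only. That range rests on 1.16% annual mortality, no loss to follow-up, no ageing and an assumed cardiac share of 10-40%. A reader might infer a firm minimum number of lost events from the mortality rate. The documents do not support one, because the lower limit is zero and they give no cardiac share.

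The effect is confined to the secondary cardiac and aspirin-resistance models and to the fatal SAE tables. Severity is minor.

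**What to change.** In the SAP:

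1. Define the cardiac outcome as the first cardiac SAE or cardiac death by recorded cause. Take cause from the Death form, and from registry flagging only where it gives a cause. Name the source form for cause of death in Appendix 2.
2. Count each patient once.
3. State the time window and apply it alike to fatal and non-fatal events in the main definition. One option is on medication plus 30 days, with cardiac deaths over all follow-up as a sensitivity analysis.
4. In section 11, show Death-form deaths by arm beside the fatal SAE tables.

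Also reconcile the protocol's Summary Schedule of Events with sections 6.5, 10.1 and 10.8 on which form a death uses, and Protocol section 10 with SAP section 11 on when SAE recording ends. The last visit is set for February 2017 (plus 3 months) and the final analysis starts in September 2017, so rewording the protocol will not move forms already sent. The SAP definition has to do the work.

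The cost is SAP wording and a check of Death forms for cardiac cause. No new data collection is needed: cause of death is already a listed variable and is required for the oesophageal-cancer death outcome. This is a free improvement.

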Scientific rationale:	
The role of aspirin in the prevention of not only colorectal cancer but also oesophageal adenocarcinoma is already accepted in epidemiological studies (19 - 22). Although aspirin is already being used prophylactically in premalignant colorectal lesions, a study of its application to BM is urgently needed. PPIs are used widely but their efficacy in chemoprevention is unclear and if there is an effect the most cost-effective dose is not known. Esomeprazole is arguably the leading agent in its class.
	
Clinical rationale:	
Conventional clinical risk factors for BA have not been proven in randomised controlled studies, although males have an excess risk of oesophageal adenocarcinoma compared with females at a ratio of 3 to 1 (6 - 16). In the absence of proven stratification, surveillance of all cases of BM is required; this is neither feasible nor cost effective (17). Primary prevention strategies should be aimed at reducing the initiation and malignant degeneration of BM by pharmaceutical manipulation of the oesophageal environment.
	

	Potent acid suppressing drugs and aspirin for chemoprotection have the greatest applicability.	
Primary Endpoint:	A composite primary endpoint of all-cause mortality and conversion to adenocarcinoma and conversion to high grade dysplasia.	
Secondary Endpoints:	
 
• All-cause mortality
 
• Conversion to oesophageal adenocarcinoma
 
• Conversion to high grade dysplasia
 
• Death from oesophageal cancer
 
• Cost/oesophageal adenocarcinoma prevented
 
• Cost/life year saved
 
• Molecular markers to be identified at the end of the trial and used during analyses of collected blood and/or tissue samples
 
• Cost/quality adjusted life saved
 
• Formation of new tumours
 
• Composite endpoint of all-cause mortality and conversion to adenocarcinoma and conversion to high grade dysplasia according to gender
 
	
Study Design:	This is a pragmatic, national, multicentre, phase III, randomised 2x2 factorial controlled trial of low or high dose esomeprazole with or without low dose aspirin for 8-10 years	
Patient Numbers:	2513	
Target Population:	Patients with circumferential Barrett's metaplasia of at least 1cm in length ( $\geq$ C1M1) or a tongue of Barrett's metaplasia of at least 2cm in length ( $\geq$ COM2)	

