To assess whether intervention with PPI and/or aspirin induces changes in the expression of molecular markers for BA. To assess the genomics of aspirin sensitivity (efficacy and side effects)	
 
Molecular markers to be identified at the end of the trial and used during analyses of collected blood and/or tissue samples
 
	End of trial

To assess how quality of life is affected by the different treatments	
 
Cost/quality adjusted life saved
 
	End of trial
To assess what the biological risk factors are for cardiac disease and aspirin resistance	
 
Molecular markers to be identified at the end of the trial and used during analyses of collected blood and/or tissue samples
 
	End of trial
To assess gender differences in outcomes	
 
A composite endpoint of all-cause mortality and conversion to adenocarcinoma and conversion to high grade dysplasia
 
All-cause mortality
 
Conversion to oesophageal adenocarcinoma
 
Conversion to high grade dysplasia
 
Death from oesophageal cancer
 
	End of trial
Tertiary/Exploratory Objectives	Endpoints	
To assess aspirin's role on the development of colorectal adenomas and cancer	New tumour	End of trial
To collect and bank samples for use in future ethically approved studies	Not applicable	Not applicable

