## 13 STATISTICAL CONSIDERATIONS

### 13.1 Primary and Secondary Endpoints

**PRIMARY:** Time from randomisation to the first of the following:

- conversion from Barrett's oesophagus to adenocarcinoma of the oesophagus (event)
- high grade dysplasia (event)
- death by all causes (event)
- last known follow-up (no event)

**SECONDARY:** Time from randomisation to:

- adenocarcinoma of the oesophagus
- high grade dysplasia
- all-cause mortality
- cause-specific mortality

Also safety, quality of life, health economics, new tumours and molecular markers.

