ANALYSIS: Using the survival time calculated for the primary objective, a logrank test to assess the effect of gender with both males and females in the sample will be reported in a table as for the primary objective. Create an AFT model looking at the gender effect adjusting for age, length of Barrett's and presence of intestinal metaplasia so that there is a time ratio with 95% confidence interval for the gender effect. Repeat with a Cox model if assumptions valid. Redo both of these models with treatment also included.

Exploratory aim

To assess aspirin's role on the development of colorectal adenomas and cancer

Use as outcome the time to colorectal cancer or colorectal adenoma. Using a logrank test, consider if aspirin use is prognostic.

To collect and bank samples for use in future ethically approved studies

To be analysed under other protocols and analysis plans.

And the exploratory uses of the data

- Describe Barrett's length over repeat biopsies and investigate a change in length from baseline to 2 years between treatment groups.

ANALYSIS: For all patients, assess if Barrett's metaplasia length shows a trend with time using repeated measures anova.

Using the baseline and 2 year length, compare the Barrett's length difference between treatment groups using paired ttest.

- Can intervention with aspirin result in a lower stage of adenocarcinoma ?
Can intervention with PPI result in a lower stage of adenocarcinoma ?

ANALYSIS: Chi square trend test on the following tables

AspECT

A phase III randomised study of Aspirin and Esomeprazole chemoprevention in Barrett's metaplasia

Funded by CR-UK, MRC, UHL and NCI

ISRCTN No.85156844

	No aspirin	Aspirin
None		
Stage I		
Stage II		
Stage III		
Stage IV		

	Low PPI	High PPI
None		
Stage I		
Stage II		
Stage III		
Stage IV		

Note: this ignores the different follow-up times

- Does adjustment for oesophagectomy, ablation therapy, endoscopic mucosal resection change the treatment effect ?

ANALYSIS: Within the multivariate AFT and COX models, add time dependent variables for the above and note the new treatment effect.

- Is the event rate different for those previous users of aspirin who were not randomised to it compared to previous users who continued with aspirin as their randomised treatment?

ANALYSIS: Kaplan-Meier curve and Logrank of the previous users of aspirin who were not randomised to it versus those randomised to aspirin.

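### New tumours are listed as a secondary endpoint, but the SAP plans no randomised comparison of new tumours of any site, and none by PPI dose on any tumour outcome beyond the oesophagus.

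*SAP*

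**What the plan says.** The status of new tumours differs from place to place.

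- The protocol synopsis lists "Formation of new tumours" among the secondary endpoints, with no site limit.
- Protocol 13.1, under its secondary heading, adds: "Also safety, quality of life, health economics, new tumours and molecular markers".
- The table in Protocol 3 gives new tumour as the endpoint of one objective only, which is exploratory: "To assess aspirin's role on the development of colorectal adenomas and cancer".
- SAP 2.7 keeps new tumours among the secondary outcomes, in the line "Cardiac event from SAE (our best data on cardiac disease) and new tumours (a marker of aspirin resistance".

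SAP section 9 analyses new tumours of any site under the aim on cardiac disease and aspirin resistance. It first sets out cardiac models: "The risk factors to be tested are hypercholesterol, family history of cardiac disease, patient history of cardiac disease, hypertension, diabetes or smoking". For aspirin resistance, "a logistic model predicting cardiac disease in those taking aspirin will be built and described". It then adds: "These 2 models will be repeated for the data from the time of the new tumour questions using cancer instead of cardiac disease".

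For colorectal disease the exploratory plan is: "Use as outcome the time to colorectal cancer or colorectal adenoma. Using a logrank test, consider if aspirin use is prognostic". A further exploratory analysis fits an AFT model to time to epithelial cancer (oesophageal, colorectal, other gastrointestinal or skin), aspirin against no aspirin, in the two low-PPI arms.

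**The concern.** In a chemoprevention trial, a secondary endpoint of new tumours naturally raises the question of whether either randomised factor changes their rate. The section 9 models ask something else: whether cardiac risk factors predict cancer, overall and among aspirin takers. They could be run exactly as planned and still say nothing about aspirin or PPI dose.

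The gap is widest for PPI. SAP 2.1 and section 9 both raise the possibility that high-dose PPI increases colon cancer through gastrin, yet the analysis placed under that statement tests aspirin only. The plan thus names a possible harm of one randomised factor and specifies no test of it. Under SAP section 10, any comparison added after the data are seen is exploratory, so the omission cannot be fully repaired later.

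**Working it through.** The plan gives no figure to reproduce here. The check is to take each SAP analysis whose outcome is, or could include, a tumour and see whether it contains a randomised comparison.

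| SAP analysis | Outcome | Aspirin compared | PPI dose compared |
|---|---|---|---|
| Section 9, secondary | Oesophageal adenocarcinoma; all oesophageal cancers as sensitivity | Yes | Yes |
| Section 9, aspirin-resistance aim, first model | Cancer, from when the tumour questions began | No | No |
| Same aim, second model | As above, in those taking aspirin | No, and impossible by design | No |
| Section 9, exploratory | Colorectal cancer or adenoma | Yes, logrank | No |
| Section 9, exploratory | Epithelial cancer (oesophageal, colorectal, other GI, skin) | Yes, AFT, low-PPI arms only | No, and impossible in low-PPI arms |
| Section 9, exploratory | Stage of oesophageal adenocarcinoma | Yes | Yes |
| Section 11 | Serious adverse events | Yes | Yes, but no tumour category is named |

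For outcomes that reach beyond the oesophagus, leaving aside the generic SAE comparison, the count is:

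- new tumours of any site: 0 randomised comparisons;
- aspirin: 2 comparisons, both exploratory and both limited by site;
- PPI dose: 0 comparisons.

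Three further points follow from setting the passages side by side.

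1. SAP 2.7 and section 9 attach new tumours to the objective on cardiac disease and aspirin resistance. In Protocol 3 the endpoint of that objective is molecular markers, so the pairing does not come from the protocol's table.
2. The two models are logistic and so ignore time to event. The SAP analyses its other clinical secondary endpoints with AFT models, and with Cox models that allow for competing deaths where needed.
3. Restricting the epithelial analysis to the low-PPI arms uses two of the four arms. With balanced arms and similar event rates this keeps about half the events, so the standard error of the log hazard ratio rises by √2 ≈ 1.41.

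To show what halving does, take the SAP's own design values for the primary endpoint (196 events, control-to-treatment hazard ratio 1.5, two-sided 5%), with power = Φ(ln(HR) × √events / 2 − 1.96):

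- 196 events: Φ(0.405 × 14 / 2 − 1.96) = Φ(0.88) = 81%;
- 98 events: Φ(0.405 × 9.90 / 2 − 1.96) = Φ(0.05) = 52%.

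This shows the cost of using half the factorial. It is not an estimate of power for epithelial cancer, for which the documents give no event number.

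**The case against.** The strongest reply is that the endpoint's status is unsettled in the protocol itself. The Protocol 3 table ties new tumour to one exploratory question, about aspirin and colorectal disease, and the SAP does answer that question by randomised aspirin. No secondary objective in either document asks for a treatment effect on tumours of any site, and none asks about PPI dose and tumours. This stands as a reason to reconcile the passages first. It does not remove the listings in the synopsis and Protocol 13.1, and it does not explain the untested PPI hypothesis.

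A reader might infer that aspirin is never compared on tumours. The documents do not support that, because the colorectal and epithelial analyses are both aspirin comparisons. Nor can one say that PPI dose is compared on no cancer: oesophageal cancer is compared by PPI dose as a secondary outcome.

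Serious tumours could also surface in the SAE comparison, which is made for both factors. That is a partial safeguard only: no tumour category is named, and SAP section 11 ends recording when trial medication stops.

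The low-PPI restriction may be deliberate, to keep a possible PPI effect out of the aspirin estimate. Adjusting for randomised PPI dose would do the same without discarding half the patients, unless the two factors interact.

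Finally, counting from when the tumour questions began weakens the protection of randomisation. It compares patients still in follow-up and tumour-free at that date, in an open-label trial (SAP 2.6.2). That limit is real and belongs in the report.

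**Conclusion.** The point holds in this form: followed as written, the plan leaves a listed secondary endpoint, new tumours of any site, without a randomised comparison. It also leaves the SAP's own hypothesis about high-dose PPI and colon cancer untested. For aspirin the gap is partial, since two exploratory, site-limited comparisons exist. For PPI dose it is complete beyond the oesophagus, apart from the generic SAE comparison. This affects a secondary endpoint, not the primary, and should be corrected before the final analysis.

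The conclusion rests on the text alone and assumes that the section 9 models contain only the predictors listed. A reader might want a power for the missing comparisons, but the documents do not support one. They give no rate for new tumours and no start date for the tumour questions, the planned colorectal outcome counts adenomas as well as cancers, and the aspirin set is smaller than 2513 because patients in the PPI-only randomisation are excluded from it.

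**What to change.** 1. Reconcile the status and definition of new tumours across the protocol synopsis, Protocol 3, Protocol 13.1 and SAP 2.7. State whether the endpoint is secondary or exploratory and which tumours count, and drop the aspirin-resistance label as its definition.
2. In SAP section 9, add time to first new tumour, compared by randomised aspirin (the aspirin ITT set) and by PPI dose (all randomised). Use the adjusted AFT and competing-risks Cox methods already specified for secondary endpoints, with delayed entry from when the tumour questions began, and give that date.
3. Add the PPI-dose comparison to the colorectal and epithelial cancer analyses. For the epithelial aspirin comparison use all aspirin-randomised patients, adjusted for PPI dose.
4. Keep the cardiac-risk-factor models if wanted, described as prognostic models.

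The cost is SAP wording and a few model runs on data the SAP already plans to use; how complete those data are is not stated. The downsides are a few more secondary or exploratory comparisons, to be labelled as such, and the delayed-entry limitation, to be stated with the results.
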